Patient demographic data and patient-reported outcomes will be collected using the DOD's Pain Assessment Screening Tool and Outcomes Registry (PASTOR).⁶² This Web-based patient-reported outcomes tool, currently used at Madigan IPMC,⁶³ was designed to reduce the burden of patient questionnaires during clinical contact through modern information technology and to make use of **well-established and validated pain-related assessments** already available. It uses the computerized adaptive learning system of the Patient Reported Outcome Measurement Information System (PROMIS), which contains a large, validated databank of all surveys from the literature and was developed by the National Institutes of Health (NIH). Notably, PASTOR is one of the major recommendations from the 2010 Army Pain Management Task Force Report. PASTOR will serve two major purposes: first, it will collect longitudinal outcomes data on patients treated in military hospitals in an outcomes registry; and second, it will provide a summary outcomes report on each patient for the IM and FR clinical team for review at during each assessment period. The PASTOR outcomes report (which includes the specific outcomes and treatment data collected) is presented in Section 6: Surveys, Questionnaires, and Other Data Collection Instruments – PASTOR. It is currently beginning a beta-test phase in select Army and Navy medical treatment facilities (including MAMC), and will be implemented during 2015-16 as standard of care for pain assessment at Army hospitals nationwide.

All patients will complete scheduled assessments according to the following timeline of the study:

1. At baseline, prior to randomization to SC or IM
2. At completion of SC or IM, prior to initiation of FR program
3. At completion of FR program

4. At 3-months post-FR program

5. At 6-months post-FR program

Table 3. Patient-Reported Outcome Measures in PASTOR

Primary Outcomes

Defense and Veterans Pain Rating Scale (DVPRS)⁶⁴

- Pain Intensity 10-pt Numeric Rating Scale (NRS)

Physical Function Subscale of PROMIS Global Health⁶⁵

Secondary Outcomes

PROMIS Pain Interference⁶⁶

PROMIS Depression⁶⁷

PROMIS Anxiety⁶⁷

PROMIS Emotional Distress - Anger⁶⁷

PROMIS Sleep Disturbance⁶⁸

PROMIS Fatigue⁶⁹

Patient-defined activity goal⁷⁰

Patient Activation Measure (PAM)⁷¹

Drug Use Questionnaire (DAST-10)⁷²

Pain Catastrophizing Scale (PCS)⁷³

Tampa Scale for Kinesiophobia (TSK11)⁷⁴

Pain Self Efficacy Questionnaire (PSEQ)⁷⁵

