11.0 Statistical/Data Analysis Plan

11.1 Statistical Considerations:

List the statistical methods to be used to address the primary and secondary objectives, specific aims, and/or research hypotheses. Explain how missing data and outliers will be handled in the analysis. The analysis plan should be consistent with the study objectives. Include any sub-group analyses (e.g., gender or age group). Specify statistical methods and variables for each analysis. Describe how confounding variables will be controlled in the data analysis

The statistical methods that will be used for each study aim are explained in section 11.3.

Approach to Missing Data.

The amount of missing data will be first quantified where possible, and determined by the amount of missing data that occurs, three indirect tests of the mechanism of missingness will be explored: (1) baseline demographic characteristics of those who ever and never missed data by group allocation will be compared (an indirect test to rule out missing completely at random [MCAR]); (2) the difference between mean utility scores of participants with missing and non-missing data will also be compared (an additional indirect test to rule out MCAR) and (3) controlling for the probability of providing missing data, the mean scores of those that never and ever missed in intervention and control groups will be compared (an indirect test of missing not at random [MNAR]). While analysis using mixed models allows all observed data to be included in the analysis under the assumption that the data are MCAR, if substantial missing data occurs, multiple imputation or mean conditional imputation will be used with subsequent sensitivity analyses to explore the impact of imputation on results. To address the issue of artificially reduced estimates of stochastic uncertainty produced by imputation, bootstrapping procedures will be used on the entire imputation and estimation process.

11.2 Sample Size Estimation:

Estimated required sample size: 152
Estimated participant drop out + withdrawal: 28%
Total enrollment requirement: 210
Total MAMC enrollment: 210

11.3 Data Analysis Plan:

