Primary (i.e., primary outcome variables) and secondary endpoints. The primary outcome endpoints are pain intensity and functional status as measured by the PASTOR questionnaire. In addition, secondary predictors of outcomes measures will be evaluated, including demographic factors (age, military rank, household income, race), measures of pain interference, depression, anxiety, anger, sleep quality, fatigue, medical board status for disability, duration of pain-related disability, prescription opioid dosage and functional capacity tests for endurance and strength.

Data analysis.

Aim 1: Evaluate the benefit of a program of multimodal integrative pain management therapies prior to an intensive functional restoration program, relative to standard care.

Hypothesis: Patients who complete an IM program prior to an FR program will demonstrate significantly greater improvements in pain and physical function going into the FR program, relative to standard care. At post-FR, patients who completed an IM program prior to FR will demonstrate significantly improved outcomes on pain severity and physical function at discharge from the program and at 3-months post-FR, relative to standard care.

Analytical Technique: We will use a hierarchical linear model (HLM) for a cluster-randomized trial with time nested within patients.⁷⁷ HLM affords an integrated approach to studying the structure and predictors of individual change, and provides the appropriate standard errors and correct statistical inferences for clustered data. HLM models allow the use of data from patients who are missing one or more observations, where the assumption holds that data are missing at random. Some patients will not follow the intervention protocol, either deliberately by not doing the intervention or due to extenuating circumstances that prevent their participation with the intervention protocol. We will use an intent-to-treat analysis.

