We will initially complete analyses without the inclusion of pre-randomization covariate information. In all analyses, the data will be examined for appropriateness of the statistical assumptions underlying fitted models (e.g., distribution of regression residuals, identification of multivariate outliers representing influential data points, tests for departures from linearity). The primary analysis will examine differences between the control and intervention groups' outcome scores at the 3 month assessment point. To control for inflation of Type I error rates due to co-primary outcomes, alpha will be set to 0.025 for each test of the outcome variables.

If recruitment targets are exceeded to a sufficient magnitude, secondary analyses of change in pain severity and physical function using responder analysis will also be performed. When consensus on minimally important difference (MID) exists, that MID will be used to define response. For PROMIS measures that do not have consensus MID measures, an improvement of one-half of one standard deviation on the PROMIS scale will be considered the minimally important difference for a positive response. Responder analyses require higher sample sizes to detect statistically significant differences but are the preferred method of assessing treatment effect, and permit meaningful comparisons between randomized clinical trials.⁷⁸

Aim 2: Identify prognostic factors that predict successful outcomes on pain severity and function following intensive interdisciplinary functional restoration.

In addition to IM vs standard care, secondary predictors of outcomes following FR will include baseline measures of: demographic variables (age, military rank, race, military occupation), pain characteristics (location, duration, character), psychosocial factors (depression, anxiety, anger); sleep quality and fatigue; medical board status for disability; duration of pain-related disability; prescription opioid dosage; and functional capacity tests for endurance and strength.

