Analytical Technique: The co-primary outcomes for pain severity and physical function will be analyzed using a Sequential Multiple Regression model.⁷⁹ The model will adjust for baseline measures of the co-primary outcomes and pre-FR treatment groups, before assessing the relative importance of secondary outcomes measures (baseline measures of pain interference, depression, anxiety, anger, sleep quality, fatigue, medical board status for disability, duration of pain-related disability, prescription opioid dosage, and functional capacity tests for endurance and strength). Relative importance of predictors among these secondary outcomes will be reported by their respective regression beta weight coefficients. To control for inflation of Type I error rates due to co-primary outcomes, alpha will be set to 0.025 for each test of the outcome variables in their respective regression models.

Aim 3: Evaluate the relationship between legacy paper questionnaires included in the PASTOR-plus packet with PASTOR submeasures.

We will compare legacy paper questionnaires completed by study subjects which include the Tampa Kinesiophobia Questionnaire, Patient Activation Measure, Pain Self-Efficacy Questionnaire, Chronic Pain Acceptance Questionnaire and Roland-Morris Disability Questionnaire, and Pain Catastrophizing Scale with PROMIS measures included in the electronic PASTOR assessment, including pain interference, depression, anxiety, anger, and physical function. This will determine if there are legacy questionnaires with prognostic value which should be added to PASTOR.

Analytical Technique: We will use correlation analysis to determine the relationship between legacy paper questionnaires and PASTOR submeasures.

Aim 4: Evaluate the relationship between self-reported physical function (from PASTOR) and clinician-supervised tests of physical function, such as exercise treadmill test at all timepoints.

We will compare self-reported physical function with clinician-supervised tests of physical function to determine if PASTOR respondents over or under-estimate their physical capacity.

Analytical Technique: We will use correlation analysis to explore the relationship between self-report and clinician supervised tests of physical function.

Aim 5: Determine whether outcomes differ between the subgroup of participants who completed FR program 4 days per week x 3 weeks vs 2 days per week x 6 weeks.

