During the course of the study, a protocol modification was approved to allow subjects to participate in the FR program with an extended 2 days per week over 6 week schedule with the same number of treatment hours as the original 4 days per week for 3 weeks. We will evaluate outcomes in both groups to determine if one treatment approach yielded superior outcomes to the other.

Analytical Technique: We will use a Sequential Multiple Regression model.⁷⁹ We will assess the relative importance of the FR delivery method (either 4 days per week x 3 weeks vs. 2 days per week x 6 weeks controlling for treatment group on our primary outcomes of pain and physical function as well as on the secondary outcomes measures (depression, anxiety, anger, sleep quality, fatigue, medical board status for disability, duration of pain-related disability, prescription opioid dosage, and functional capacity tests for endurance and strength).

Aim 6: Compare outcome measures collected within narrow timelines to those collected within flexible timelines.

We attempted to collect outcome measures at the following timepoints: 1) within one month before starting treatment; 2) within the last day of pre-FR stage through the first day of FR stage; 3) on the last day of FR; 4) 3- and 5) 6- months after the end of FR. However, this precise collection schedule was not always possible. For example, baseline measures were collected more than one month before the start of treatment for study subjects who had conflicts such as military training exercises, personal or family illness or planned leisure travel which postponed the start of study treatment. Collection of follow-up measures was sometimes earlier or later than desired when study subjects with conflicts were unavailable at the time outcomes were requested. We plan to compare outcomes collected within the above timeframes with those collected within timeframes with modest and moderate flexibility as outlined in the following table. This analysis will inform the design of future pragmatic clinical trials in determining acceptable timeline parameters for collection of pain outcomes.

	Baseline	End of pre-FR stage	End of FR stage	Short-term	Intermediate-term
Narrow timelines	w/in 1 month of treatment start	Last day of pre-FR up to start of FR	Last day of FR	3 months after end of FR	6 months after end of FR

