Modest flexibility	w/in 2 months of treatment start	\leq 2 treatment days before end of pre-FR, through \leq 2 treatment days after start of FR	\leq 2 treatment days before end of FR, through \leq 7 calendar days after end of FR	2-4 months after end of FR	5-7 months after end of FR
Moderate flexibility	w/in 3 months of treatment start thru 2 days after treatment start	\leq 2 treatment days before end of pre-FR, through \leq 4 treatment days after start of FR	\leq 2 treatment days before end of FR, through \leq 30 calendar days after end of FR	1-<5 months after end of FR	6-9 months after end of FR

Analytical Technique: We will use a Sequential Multiple Regression model.⁷⁹ We will assess the relative importance of the timing of assessments on our primary outcomes of pain and physical function as well as on the secondary outcomes measures (pain interference, depression, anxiety, anger, sleep quality, fatigue, medical board status for disability, duration of pain-related disability, prescription opioid dosage, and functional capacity tests for endurance and strength). We will code an indicator variable to document every observation that occurs within the narrow timeline. We will use an interaction term of this indicator with the intervention to see if the intervention shows a differential effect for those who adhere to the narrow assessment timelines.

Aim 7: Determine if patient activation, pain catastrophizing, self-efficacy or pain acceptance moderate or mediates pain and function outcomes.

We will determine if level of patient activation, catastrophizing, self-efficacy and pain acceptance as measured by legacy questionnaires completed by study subjects have an impact on pain and functional outcomes.

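### No baseline-adjusted Aim 1 model is specified, so the primary 3-month comparison forgoes precision that pre-randomisation pain and function scores could supply

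*Combined protocol and SAP*

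**What the plan says.** Section 11.3, Aim 1, names an HLM with repeated times nested within patients, analysed by intention to treat. It then states: "We will initially complete analyses without the inclusion of pre-randomization covariate information". The primary contrast follows: "The primary analysis will examine differences between the control and intervention groups' outcome scores at the 3 month assessment point". This is a comparison of levels at one visit, with alpha 0.025 for each of the two co-primary outcomes. The reason given for the HLM is partly missing data: "HLM models allow the use of data from patients who are missing one or more observations". Section 11.2 gives 152 required, 210 to enrol, and "Estimated participant drop out + withdrawal: 28" per cent.

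The baseline scores are available. The assessment list in section 10.1 opens with "At baseline, prior to randomization to SC or IM". Aim 2, the prognostic regression, uses them: "The model will adjust for baseline measures of the co-primary outcomes and pre-FR treatment groups".

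The timing of baseline varied. Under Aim 6 the plan reports that for some subjects "baseline measures were collected more than one month before the start of treatment". The widest baseline window in the Aim 6 table is "w/in 3 months of treatment start thru 2 days after treatment start".

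**The concern.** The word initially leaves room for a later adjusted analysis, but sections 11.1 to 11.3 contain no such Aim 1 model, no covariate list and no fixed-effect structure. At least three treatments of the baseline score fit the text: as a covariate, as a first visit with arm means constrained equal, or as a first visit with arm means left free. They do not have the same precision and can give different estimates and p-values.

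Two things are at stake. The first is efficiency: pain and function measured before randomisation usually predict the same scores later, and an analysis that ignores this has a larger standard error than it needs. The second is pre-specification: if the primary model is not fixed in writing, it can be chosen once results are known.

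A smaller gap follows. Any adjusted model needs a rule for which score is baseline. A score taken after treatment has started is post-randomisation and should not serve as a baseline covariate. The Aim 1 text gives no rule.

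**Working it through.** **Inputs from the documents.** Required N 152, dropout 28%, enrolment 210 (section 11.2); alpha 0.025 per co-primary outcome (section 11.3, Aim 1); five assessments, the first before randomisation (section 10.1).

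**Assumptions, not in the documents.** Allocation 1:1 (76 per arm for 152, 105 per arm for 210); two-sided tests; true effect 0.5 SD; baseline to 3-month correlation r = 0.2, 0.3, 0.5 or 0.6.

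**The plan's own figures.** 152 / (1 − 0.28) = 211.1, or 212 in whole pairs, against the stated 210, which is close enough. The plan gives no derivation of 152. An unadjusted two-sample comparison of 0.5 SD at two-sided alpha 0.025 and 80% power needs 2 × (2.241 + 0.842)² / 0.5² = 76.04 per arm, rounded up to 77, or 154 in total. So 152 fits an unadjusted design, with little margin.

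**Complete data.** Unadjusted variance of the 3-month difference: 2σ²/n. Adjusted for baseline: (2σ²/n)(1 − r²). With n = 76 per arm and t-test power:

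| r | 1 − r² | Power at 0.5 SD | Detectable effect at 80% power |
|---|---|---|---|
| unadjusted | 1.00 | 79.2% | 0.504 SD |
| 0.2 | 0.96 | 81.0% | 0.494 SD |
| 0.3 | 0.91 | 83.2% | 0.481 SD |
| 0.5 | 0.75 | 90.1% | 0.437 SD |
| 0.6 | 0.64 | 94.3% | 0.403 SD |

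**Does the HLM already capture this?** With complete data and a free mean for each arm at each visit, the generalised least squares (GLS) variance of the 3-month contrast equals the unadjusted variance (ratio 1.00 at r = 0.3, 0.5 and 0.7). Constraining the arms to be equal at baseline gives 0.91, 0.75 and 0.51, which is exactly 1 − r².

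**With dropout.** GLS with 105 per arm, five visits, visit-by-group means and compound symmetry. The 28% is lost before 3 months, spread evenly over the three intervals between baseline and 3 months. Power uses the normal approximation.

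| r | Free-mean HLM: variance cut against completers' t-test | Constrained baseline: further cut | Power, free | Power, constrained |
|---|---|---|---|---|
| 0.2 | 1.9% | 2.9% | 80.6% | 81.8% |
| 0.3 | 3.9% | 6.7% | 81.4% | 84.3% |
| 0.5 | 9.2% | 19.8% | 83.8% | 91.3% |
| 0.6 | 12.4% | 29.6% | 85.2% | 95.3% |

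A free-mean HLM therefore recovers some precision through patients with missing visits, but not most of it. Placing all dropout straight after baseline, or all of it after FR, changes the further cut only to 2.9–3.0%, 6.6–6.8%, 19.4–20.1% and 28.8–30.1%. A correlation that decays with time moves these figures by under 0.2 points.

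**The case against.** The strongest reply is that loss of precision is not proved, because the HLM's fixed effects are not stated. The plan speaks of individual change, baseline is the first scheduled assessment, and pre-randomisation covariates could mean demographic and clinical variables rather than the outcome's own first value. The size also depends on the model. In a linear growth model with a random intercept, free group intercepts and assumed visits at weeks 0, 3, 6, 19 and 32, power at 0.5 SD is already 99.7%, 99.3%, 97.8% and 96.8% at the four values of r, so at most about 3 points remain to be gained.

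That stands as a caution about the power figures. It does not remove the point. The growth model relies on linear change and no random slopes, neither of which the plan states, and a baseline constraint would still cut its variance by 26% to 68%. Whether the HLM handles baseline efficiently is exactly what the plan leaves unsaid.

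It is also fair that the issue is efficiency and not validity, and that 152 is consistent with an unadjusted design. The trial may have been sized for the analysis it describes. But an available gain at no cost is still worth taking, and about 79% to 80% power leaves little slack.

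On baseline timing, section 10.1 does place baseline before randomisation, the wide window belongs to Aim 6, and an early score is not a post-randomisation one. This part is secondary: it is a rule that an adjusted model would need, not an error in Aim 1.

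Finally, the plan does fix the order of analyses, the time point and alpha, and nothing in it says that an adjusted model would replace the unadjusted one. It does not rule that out either.

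**Conclusion.** The concern holds. The Aim 1 primary analysis is described without baseline adjustment, no adjusted model is specified, and the handling of the baseline score in the HLM is left open. The comparison as written is valid and controls type I error. What it gives up is precision: 4% to 36% of the variance with complete data for r from 0.2 to 0.6, and about 3% to 30% relative to a free-mean HLM with 28% dropout. In power for a 0.5 SD effect, that is about 1 to 2 points at r = 0.2 and 10 to 15 points at r = 0.6. These figures rest on the assumed r, effect size, 1:1 allocation and two-sided testing; the dropout figures also assume categorical visits and all dropout before 3 months. The documents cannot place r within the range. This should be changed, but it does not threaten the trial's validity.

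**What to change.** In section 11.3, Aim 1, state for each co-primary outcome that the primary estimate is the 3-month group difference from the HLM with visit as a category, group-by-visit terms, and adjustment for the pre-randomisation value of that outcome. An equally good choice is to keep baseline as the first visit and constrain its mean to be equal across arms, which also retains patients with no valid baseline. Name one of the two. State that only scores taken before randomisation count as baseline, whatever window Aim 6 explores. Keep the unadjusted analysis as a sensitivity analysis. The change should be dated before any outcome comparison by arm is seen. The cost is wording in the analysis plan; no new data, visits or patients are needed.

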To date, only one study has been published on the effectiveness of the FR program in a military patient population suffering from pain-related disability.⁶⁰ Findings from this study showed positive evidence of FR program outcomes. Participants in the FR program improved significantly compared to the standard treatment group (medication management and injection therapeutics) on self-reported pain, disability, functional status, and fitness for military duty at the post-treatment, 6-month, and 1-year follow-up points. This is the only systematic research study that has been conducted among the military personnel

using standardized functional capacity tests on endurance and lifting strength alongside patient-reported outcomes.⁶¹ **Functional restoration has extensively improved outcomes in the civilian population and prevented long-term disability while promoting a return to optimal function. To date, no studies in the military healthcare settings have identified prognostic factors for successful completion of FR, as well as maintaining satisfactory long-term outcomes. Additionally, there is insufficient published data on the potential benefits of combining FR with a course of integrative pain management modalities.**

9.4

Objectives/Specific Aims/Research Questions:

Describe the purpose and objective(s) of the study, specific aims, and/or research questions/hypotheses

Aim 1: Evaluate the benefit of a program of multimodal pain management therapies prior to an intensive functional restoration program, relative to standard care.

Hypothesis: Patients who complete an IM program prior to FR will demonstrate significantly greater improvements in pain and physical function going into the FR program, relative to standard care. At post-FR, patients who completed an IM program prior to FR will demonstrate significantly improved outcomes on pain severity and physical function at discharge from the program and at 3-months and 6-months post-FR, relative to standard care.

Aim 2: Identify prognostic factors, including demographic factors, psychologic factors, and readiness factors that predict successful outcomes on pain severity and function, as measured by the Defense and Veterans Pain Rating Scale and PROMIS functional status score, respectively, following intensive interdisciplinary functional restoration.

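### Testing 3-month pain and function at a fixed 0.025 each is valid but inefficient: Holm keeps the same 5% family-wise error and never rejects less

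*Combined protocol and SAP*

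**What the plan says.** Section 11.3 names two primary outcomes: "The primary outcome endpoints are pain intensity and functional status as measured by the PASTOR questionnaire". Under Aim 1 the primary analysis compares the arms on "outcome scores at the 3 month assessment point". The reason for the alpha rule is given as "To control for inflation of Type I error rates due to co-primary outcomes", and the rule is that "alpha will be set to 0.025 for each test of the outcome variables". No step-down or hierarchical rule follows, and the plan does not say whether success needs one outcome or both.

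The Aim 1 hypothesis also covers other time points. Section 11.3 predicts "significantly greater improvements in pain and physical function going into the FR program, relative to standard care", and then benefit "at discharge from the program and at 3-months post-FR, relative to standard care". Section 9.4 likewise predicts that "patients who completed an IM program prior to FR will demonstrate significantly improved outcomes on pain severity and physical function at discharge", and its list goes on to include 6 months, which the version in 11.3 does not. No multiplicity rule is given across time points.

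Section 11.2 gives a required sample size of 152, dropout and withdrawal of 28%, and enrolment of 210, with no design assumptions behind them.

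**The concern.** The hypothesis is about pain and physical function together, and a fixed split penalises exactly that case. Suppose the 3-month p-values are 0.001 for pain and 0.04 for function. The stated rule calls function negative. Holm tests the smaller p-value at 0.025 and, if it passes, the larger at 0.05, so it calls both positive at the same 5% family-wise error. If the sponsor instead means that both outcomes must be positive, no split is needed at all. Under either meaning of co-primary, a rule at least as powerful is available without adding patients.

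A second, smaller matter is the status of the other time points. Differences before functional restoration (FR), at discharge and at 6 months are predicted in the language of significance, but the plan does not label them secondary or place them in a testing order.

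**Working it through.** **Inputs from the documents.** Two outcomes at 0.025 each (11.3); 152 evaluable and 210 enrolled with 28% loss (11.2); two arms (10.1).

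**Inputs assumed, because the documents do not state them.** 1:1 allocation, so 152 / 2 = 76 per arm; two-sided tests; 0.5 SD on both outcomes; correlation r between the outcomes of 0.3 to 0.7. The half-SD in 11.3 is a responder threshold, so it does not establish the design effect.

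**The plan's own figures.** 152 / 0.72 = 211.1 and 210 × 0.72 = 151.2, so the dropout step agrees with 210 to within about one patient. The 152 cannot be derived from stated inputs. The assumed set fits it: n per arm = 2 × (2.2414 + 0.8416)² / 0.5² = 76.04. Other sets fit as well, for example 0.571 SD with 90% power at 0.025, or 0.486 SD with 85% power at 0.05.

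**Validity of Holm.** If both nulls are true, an error needs the smaller p-value to be at or below 0.025, which has probability at most 2 × 0.025 = 0.05. If one null is true, rejecting it needs its p-value to be at or below 0.05. The family-wise error is therefore at most 5% in every case. Every Bonferroni rejection is also a Holm rejection.

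**Power.** The mean of each test statistic is 0.5 × √(76/2) = 3.082. Critical values are c₁ = 2.2414 (two-sided 0.025) and c₂ = 1.9600 (two-sided 0.05). Power per outcome at 0.025 is Φ(3.082 − 2.241) = 80.0%.

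- Bonferroni, both: P(Z₁ > c₁, Z₂ > c₁)
- Holm, both: P(Z₁ > c₁, Z₂ > c₂) + P(Z₁ > c₂, Z₂ > c₁) − P(Z₁ > c₁, Z₂ > c₁)
- Both required, each at 0.05: P(Z₁ > c₂, Z₂ > c₂)

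Check by hand at r = 0: power at 0.05 is Φ(1.122) = 86.9%. Bonferroni gives 0.80² = 64.0%, and Holm gives 2 × 0.80 × 0.869 − 0.640 = 75.0% (75.1% without rounding).

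| r | Bonferroni, both | Holm, both | Gain (points) | Each at 0.05, both |
|---|---|---|---|---|
| 0 | 64.0% | 75.1% | 11.1 | 75.5% |
| 0.3 | 66.6% | 76.5% | 9.9 | 77.2% |
| 0.5 | 68.7% | 77.8% | 9.1 | 78.6% |
| 0.7 | 71.3% | 79.4% | 8.1 | 80.4% |
| 0.9 | 75.0% | 81.4% | 6.5 | 83.1% |

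By symmetry the gain for a single outcome is half the gain for both: 9.9 / 2 to 8.1 / 2, or about 4 to 5 points. The chance of at least one rejection is the same under the two rules, because Holm's first step is the Bonferroni test.

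**Sensitivity.** With 76 per arm and r from 0 to 0.9, the gain is 7.5 to 8.3 points at 0.3 SD, 8.6 to 12.3 at 0.4, 7.8 to 12.6 at 0.45, 6.5 to 11.1 at 0.5 and 3.3 to 5.8 at 0.6. With one-sided tests at 0.5 SD and r = 0.3 to 0.7 it is 8.7 to 7.0. The gain is never negative.

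**Other time points.** Section 11.3's list leaves four tests outside 3 months (two outcomes, before FR and at discharge); 6 months makes six. If 0.025 applies to each and the tests are independent, the chance of at least one false claim is 1 − 0.975⁴ = 9.6% or 1 − 0.975⁶ = 14.1%. For test correlations of 0.7 to 0.3, simulation gives 6.9-9.0% and 9.0-13.0%.

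**The case against.** The strongest reply is that nothing is wrong. The plan names one primary time point and divides 5% between two outcomes, which controls the primary family. Preferring Holm is a matter of efficiency, and it does not change the chance of showing at least one effect. Power for both is also the measure that flatters Holm most. All of this stands.

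Three stronger readings are tempting, and the documents do not support them.

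- A reader might infer that the plan loses 8 to 10 points of power as a matter of fact. Section 11.2 states no power, effect size, sidedness or correlation, and several design sets fit 152, so the figure is conditional.
- A reader might infer that the other Aim 1 time points have no error control at all. The 0.025 wording is not limited to 3 months and may apply to every test. What is missing is control across time points, and with 3 months declared primary the other comparisons read naturally as secondary.
- A reader might infer that each outcome's other time points could open once that outcome passes at 3 months. Combined with Holm, this spends the same alpha twice. If 3-month pain is strongly positive while 3-month function and pain before FR are null, function is tested at 0.05. With the gated test at 0.025, the error is 1 − 0.95 × 0.975 = 7.4% if independent; at 0.05 it is 1 − 0.95² = 9.75%.

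It is also fair to say that Holm is not the right rule if both outcomes are required. The success criterion has to be stated first.

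**Conclusion.** This is a cheap improvement, not a defect. That Holm dominates the fixed split at the same 5% needs no assumption about effects or correlation. The size does: about 8 to 10 points of power to show both effects, given 76 per arm, 0.5 SD on both outcomes, two-sided tests and r of 0.3 to 0.7; about 3 to 13 points for common effects of 0.3 to 0.6 SD and r of 0 to 0.9. The primary family is already controlled at 5%. For the remaining Aim 1 comparisons, the plan needs a statement of their status and one consistent list of time points.

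**What to change.** In section 11.3, Aim 1:

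1. State whether success means one positive outcome or both.
2. If one is enough, replace the fixed 0.025 rule with: *the two 3-month comparisons are tested by the Holm procedure at an overall two-sided 5%.* If both are required, test each at two-sided 0.05.
3. Label the comparisons before FR, at discharge and at 6 months as secondary, reported as estimates with confidence intervals. If they are to be confirmatory, open them only after both 3-month tests succeed, in one fixed order at 5%.
4. Reconcile the 6-month time point between sections 9.4 and 11.3.

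The change costs a few sentences and no patients. Section 11.3 (Aim 6) describes outcome collection in the past tense, so the change should be a dated amendment made before outcomes are compared by arm. There are two downsides. Holm has no simple matching simultaneous confidence intervals, so unadjusted 95% intervals would be shown and described as such. The confirmatory option in step 3 also makes the pre-FR comparison, which is closest to the intervention, depend on a 3-month contrast. Section 10.1 offers controls the integrative modalities after FR, which may dilute that contrast. This favours leaving the other time points as estimates.
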